6.1. Safety Outcomes of Concern: Rationale and Definition

With the aim of reducing potential risks associated with filgotinib, the HCP guide will address:

- Serious and opportunistic infections
- Herpes zoster
- Embryoletality and teratogenicity
- Impaired spermatogenesis
- Venous thromboembolism (VTE)
- Major adverse cardiovascular events (MACE)
- Use in the very elderly (≥ 75 years)

The summary of product characteristics (SmPC) states that patients with active tuberculosis (TB), active serious infections, or those women who are pregnant are contraindicated for treatment with filgotinib. Furthermore, patients aged 75 and older should have a starting daily dose of 100 mg as should patients with moderate or severe renal impairment (stages 3 or 4; creatinine clearance [CrCl] 15 to <60 mL/min). Screening activities include screening for TB and viral hepatitis as well as blood tests including neutrophil and lymphocyte counts, hemoglobin and lipid parameters. Further to this, the SmPC includes warnings that MACE, VTE and serious and

opportunistic infections are important safety concerns; infections are considered the main risk of immunomodulatory therapy. The following definitions are applied for these outcomes:

- MACE: Includes fatal and nonfatal CVD events. CVD comprises coronary heart disease (angina, myocardial infarction), congestive heart failure, cerebrovascular disease and peripheral artery disease.
- VTE: Includes deep venous thrombosis (DVT) and pulmonary embolism (PE).
- Serious and opportunistic infections: Opportunistic infections occur among people with weakened immune systems; such infections may be mild in people with healthy immune response but can be more serious among patients who are using immune-modulatory therapy. The overall rate of treatment-emergent serious adverse events (SAEs) at 200 mg (integrated safety summary) for serious infections was around 3.0%, among which the rate for pneumonia was 0.8%; opportunistic infections were 0.2%. The list of preferred terms in MedDRA currently comprises 192 terms under “Serious and Opportunistic infections”.

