8.3. Variables

8.3.1. Baseline Variables

Baseline variables are collected at index date. These variables reflect the patient's demographics and status at the initiation of filgotinib treatment including relevant medical history at or prior to the index date. Age (or date of birth), sex, disease duration and DAS28 are recorded at baseline for all registries.

Risk factors for MACE, VTE, and Serious and Opportunistic Infections

Variables will be collected at baseline to define the risk of each of the 3 outcomes of concern: MACE, VTE, and serious and opportunistic infections (see definitions in Section 6.1 and Annex 4).

The set of risk factor definitions were derived utilizing broader representation than that solely included in the RMP and then checked against data availability in each registry. The set of risk factors are provided in tables in each of the registry-specific sections, which reflect the availability of variables for each registry.

For MACE, the UK's Q-Risk score was used as a guide (Hippisley-Cox et al., 2008). We note that RA is a risk factor for MACE/CVD implying that the indicated patient population are at higher risk than the general population (after adjusting for age and sex). RA is available in all registries as a risk factor, as all patients have RA.

For VTE, the Jyseleca RMP mentions the following risk factors for VTE: "*prior history of VTE, advanced age, hormone replacement treatment, obesity, smoking, cancer or immobilization*". These risk factors are supplemented by considering the Caprini Score (Bahl et al., 2010), a perioperative assessment tool for new VTE. The Caprini Score highlighted the importance of a lack of mobility and hospitalization have on VTE risk.

For serious and opportunistic infections, the RMP highlighted that patients with RA were at increased risk and that the "*The reasons are multifactorial, including a poorly functioning immune system and concomitant use of immunosuppressant medications such as glucocorticoids*". The use of immunomodulators implies that patients initiating filgotinib are already at increased levels of risk. The set of risk factors for infection were supplemented by those indicated by the Rheumatoid Arthritis Observation of Biologic Therapy (RABBIT) Risk Score for serious infections (Zink et al., 2014).

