8.3.1.1. ARTIS

Patient Baseline Characteristics

Baseline variables will include the following:

- Age (at baseline)
- Sex
- Renal impairment
 - Stage (if available)
- Date of initiation of filgotinib
- Initial dose of filgotinib
- First ever administration of filgotinib: y/n
- Previous RA treatment immediately prior to initiation of filgotinib
- Date of diagnosis of RA (year; approximate if greater than 10 years earlier)
- Current severity of RA
 - Disease Activity Score (DAS):
 - DAS for 28 joint count (DAS28)
 - DAS28 type: Erythrocyte Sedimentation Rate (ESR); C-reactive protein (CRP)
 - CRP value
 - ESR value
 - Health Assessment Questionnaire (HAQ) score
 - Visual analogue scale (VAS; patient assessment of disease)
 - RA type (seropositive, seronegative)
 - Date of assessment

Risk Factors for MACE, VTE, and Serious and Opportunistic Infections

As previously described, each registry was assessed for the availability of the set of potential risk factors for the 3 endpoints of concern. In ARTIS there are no measures of obesity or immobility, both risk factors for VTE, although HAQ could be used as a proxy.

Table 3 Risk Factors for MACE, VTE and Serious and Opportunistic Infections as Available in ARTIS

	MACE	VTE	Serious and Opportunistic Infections
History of cardiovascular disease	Yes		
History of VTE		Yes	
Previous serious infection			Yes
Age	Yes	Yes	Yes
Sex	Yes		
Diabetes type 1	Yes		Yes
Diabetes type 2	Yes		Yes
Atrial fibrillation	Yes		
Chronic kidney disease	Yes		Yes
Smoking	Yes	Yes	
Family history CVD	Yes		
Use of treatment: Hyperlipidemia (Dx unavailable)	Yes		
Use of treatment: Hypertension (Dx unavailable)	Yes		
Cancer diagnosis (date)	Yes	Yes	Yes
Known thrombophilic condition		Yes	
Reduced mobility / Hospitalization (date, type, length of stay)		Yes	
Trauma and/or surgery		Yes	

	MACE	VTE	Serious and Opportunistic Infections
Ongoing hormonal replacement therapy		Yes	
Heart and/or respiratory failure		Yes	
Acute myocardial infarction or ischemic strokes		Yes	
Chronic lung disease			Yes
Glucocorticoid			Yes
TNFi			Yes
Other immunosuppressant/modifying treatment			Yes

CVD = cardiovascular disease; Dx = diagnosis; MACE = major adverse cardiovascular event; TNFi = tumor necrosis factor inhibitor; VTE = venous thromboembolism

Physician Adherence

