ANNEX 4. DEFINITION OF BASELINE DISEASES IN ARTIS, BIOBADASER, BSRBR-RA, DANBIO, AND RABBIT

The following medical code-lists were created for the long-term safety PASS (GS-EU-417-9047) and were reviewed by the registries.

	BSRBR-RA, RABBIT, BIOBADASER	ARTIS, DANBIO
Safety Risk	Operationalization (final list to be defined based on reported endpoints in each register)	Operationalization
Serious and opportunistic infections	Hospitalization and/or use of parenteral antibiotics + MedDRA Infections and Infestations SOC 10021881.	Hospitalizations in the Patient Register listing as main diagnosis ICD10codes below. If main diagnosis is RA, contributory diagnoses are also considered. A00B99 (excluding A33 and A50), D73.3, E32.1, G00G02, G04.2, G05G07, H00.0, H44.0, H60.0H60.3, H66H67, H70, I30.1, I40.0, J00J22, J32, J34.0, J36, J39.0J39.1, J44.0, J85, J86, K04.4, K04.6, K04.7, K10.2, K11.3, K12.2, K14.0, K57.0, K57.2, K57.4, K57.8, K61, K63.0, K65.0, K65.1, K65.2, K65.9, L00L08, L30.3, M00M01, M46.2M46.5, M60.0, M65.0, M71.0, M71.1, M72.6, M86, N13.6, N15.1, N15.9, N30.0, N30.8, N34.0, N41.2, N43.1, N45.2, N45.3, N45.4, N48.2, N61, N70, N73, N75.1.
Herpes zoster/ Varicella zoster	10019974 Herpes zoster, 10019983 Herpes zoster ophthalmic, 10030865 Ophthalmic herpes zoster, 10058428 Herpes zoster multidermatomal, 10063491 Herpes zoster oticus, 10065038 Herpes zoster disseminated, 10065119 Necrotising herpetic retinopathy, 10072210 Genital herpes zoster, 10074241 Varicella zoster gastritis, 10074245 Herpes zoster pharyngitis, 10074248 Herpes zoster meningoencephalitis, 10074253 Herpes zoster necrotising retinopathy, 10074254 Varicella zoster pneumonia, 10074254 Varicella zoster pneumonia, 10074259 Herpes zoster meningitis, 10074297 Herpes zoster cutaneous disseminated.	Hospitalizations in the Patient Register listing as main diagnosis ICD10codes A02, A15A19, A31, A32, A43, A48.1, B02, B38, B39, B40, B44, B45, B58, B59. If main diagnosis is RA, contributory diagnoses are also considered.
Malignancy	Malignant or unspecified tumours.	All invasive malignancies recorded in the cancer register, excluding NMSC.

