
MACE
	
Fatal and nonfatal : 10000891 Acute myocardial infarction; 10006147 Brain stem infarction; 10006148 Brain stem ischaemia; 10008034 Cerebellar infarction; 10008088 Cerebral artery embolism; 10008120 Cerebral ischaemia; 10008190 Cerebrovascular accident; 10014498 Embolic stroke; 10019005 Haemorrhagic cerebral infarction; 10019016 Haemorrhagic stroke; 10024033 Lateral medullary syndrome; 10028596 Myocardial infarction; 10028602 Myocardial necrosis; 10033697 Papillary muscle infarction; 10043647 Thrombotic stroke; 10049768 Silent myocardial infarction; 10051078 Lacunar infarction; 10055677 Haemorrhagic transformation stroke; 10056237 Migrainous infarction; 10059613 Stroke in evolution; 10060839 Embolic cerebral infarction; 10060840 Ischaemic cerebral infarction; 10061256 Ischaemic stroke; 10062573 Brain stem thrombosis; 10064961 Thalamic infarction; 10066591 Post procedural stroke; 10066592 Post procedural myocardial infarction; 10067167 Cerebellar embolism; 10067347 Thrombotic cerebral infarction; 10067462 MillardGubler syndrome; 10068621 Cerebellar ischaemia; 10068644 Brain stem stroke; 10069020 Basal ganglia infarction; 10070671 Cerebral septic infarct; 10070754 Inner ear infarction; 10071043 Basal ganglia stroke; 10071260 Carotid angioplasty; 10073945 Perinatal stroke; 10074422 Brain stem embolism.
 
Fatal only: 10002886 Aortic aneurysm rupture; 10003173 Arterial rupture; 10003210 Arteriosclerosis; 10003212 Arteriosclerosis moenckebergtype; 10006145 Brain stem haemorrhage; 10007522 Cardiac asthma; 10007554 Cardiac failure; 10007556 Cardiac failure acute; 10007558 Cardiac failure chronic; 10007559 Cardiac failure congestive; 10007559 Cardiac failure congestive; 10007560 Cardiac failure high output; 10007625 Cardiogenic shock; 10007684 Carotid arterial embolus; 10007686 Carotid artery aneurysm; 10007688 Carotid artery thrombosis; 10008023 Cerebellar artery thrombosis; 10008030 Cerebellar haemorrhage; 10008076 Cerebral aneurysm ruptured syphilitic; 10008086 Cerebral arteriovenous malformation haemorrhagic; 10008089 Cerebral artery occlusion; 10008092 Cerebral artery thrombosis; 10008111 Cerebral haemorrhage; 10008118 Cerebral infarction; 10008132 Cerebral thrombosis; 10018985 Haemorrhage intracranial; 10022758 Intracranial aneurysm; 10022840
	
Combines MI, stroke, and fatal cardiovascular events: I00I99 as main cause of death, or I20.0, I21, I60I64 as diagnosis in in or outpatient care.

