	
Intraventricular haemorrhage; 10022841 Intraventricular haemorrhage neonatal; 10024119 Left ventricular failure; 10024242 Leriche syndrome; 10034476 Pericardial haemorrhage; 10036511 Precerebral artery occlusion; 10039163 Right ventricular failure; 10039330 Ruptured cerebral aneurysm; 10042316 Subarachnoid haemorrhage; 10042434 Sudden death; 10047279 Ventricle rupture; 10048380 Aneurysm ruptured; 10048761 Atrial rupture; 10049418 Sudden cardiac death; 10049993 Cardiac death; 10050403 Carotid artery dissection; 10051093 Cardiopulmonary failure; 10051328 Carotid aneurysm rupture; 10052019 Femoral artery occlusion; 10053633 Cerebellar artery occlusion; 10053649 Vascular rupture; 10053949 Vascular pseudoaneurysm ruptured; 10055803 Haemorrhage coronary artery; 10058178 Aortic occlusion; 10060874 Aortic rupture; 10060953 Ventricular failure; 10060964 Arterial haemorrhage; 10062585 Peripheral arterial occlusive disease; 10062599 Arterial occlusive disease; 10063081 Acute left ventricular failure; 10063082 Acute right ventricular failure ; 10063083 Chronic left ventricular failure; 10063084 Chronic right ventricular failure; 10064595 Haemorrhagic arteriovenous malformation; 10064601 Iliac artery occlusion; 10065441 Venous haemorrhage; 10065558 Aortic arteriosclerosis; 10067057 Basal ganglia haemorrhage; 10067116 Carotid arteriosclerosis; 10068119 Aortic dissection rupture; 10068119 Aortic dissection rupture; 10068230 Cardiorenal syndrome; 10069694 Brachiocephalic artery occlusion; 10069695 Subclavian artery occlusion; 10069696 Coeliac artery occlusion; 10071716 Vertebral artery dissection; 10072043 Central nervous system haemorrhage; 10072789 Iliac artery rupture; 10073565 Intracranial artery dissection; 10073565 Intracranial artery dissection; 10073681 Epidural haemorrhage; 10075449 Brachiocephalic arteriosclerosis; 10076203 Radiation associated cardiac failure.
	

Venous thromboembolism (deep venous thrombosis and pulmonary embolism)
	
10037377 Pulmonary embolism; 10051055 Deep vein thrombosis; 10061408 Venous thrombosis limb; 10063909 Post procedural pulmonary embolism; 10066881 Deep vein thrombosis postoperative.
	
Main diagnosis in the Patient Register, in or outpatient component, of the following ICD10 codes: I26.9, I26.0, I80.1, I80.2, I80.3, I80.8, I80.9, I81.0, I82.0, I82.1, I82.2, I82.3, I82.8, I82.9. Or, pulmonary embolism I26.0 listed as the underlying cause of death.

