
Hyperlipidemia
	
BIOBADASER: Lipid measures LDL, HDL, total cholesterol or triglycerides may be captured according to clinical practice.
	
Patients who will initiate treatment with statins and other lipid-lowering drugs.

	
BSRBR-RA: Patients who will initiate treatment with statins or other lipid-lowering drugs.
 
RABBIT: Hyperlipidemia reported as adverse event by the treating physician.
	
--	--	--

Other medical history

Disease	Data source	ICD10
Malignancy	The Cancer register	All except benign tumors
Infection	Main diagnoses from the Inpatient component of Patient Register.	A00B99, D73.3, E06.0, E32.1, G00G02, G04.2, G05G07, H00.0, H44.0, H60.0H60.3, H66H67, H70, I30.1, I40.0, J00J22, J32, J34.0, J36, J38.3, J39.0J39.1, J44.0, J85, J86, K04.4, K04.6, K04.7, K10.2, K11.3, K12.2, K14.0, K57.0, K57.2, K57.4, K57.8, K61, K63.0, K65.0, K65.1, K65.2, K65.9, L00L08, L30.3, M00M01, M46.2M46.5, M60.0, M65.0, M71.0, M71.1, M72.6, M86, N10, N11, N12, N13.6, N15.1, N15.9, N30.0 N30.8, N34.0, N41.2, N43.1, N45.2, N45.3, N45.4, N48.2, N61, N70, N73, N75.1
Renal impairment		N18, N18.1, N18.2, N18.3, N18.4, N18.5
Knee or hip prosthesis	Operation codes from the Patient register	NGB, NFB
Diabetes	The Patient Register	E10E14, O24
Myocardial infarction	The Patient Register	I21, I22

SIGNATURE PAGE – INVESTIGATOR

Study Title: Non-interventional post-authorization cohort safety study evaluating the effectiveness of the additional risk minimization measures for filgotinib (Jyseleca®) use in patients with moderate to severe active rheumatoid arthritis within European registries

CSP Version:

1.0

Date:

02-Feb-2022

I, the undersigned, have read this non-interventional study protocol and will conduct the study as described in compliance with the study protocol, in accordance with the guidelines of Good Pharmacoepidemiology Practises and Heads of Medicines Agencies Good Pharmacovigilance Practices.

Investigator Name

Signature

Date

SIGNATURE PAGE – SPONSOR

Study Title: Non-interventional post-authorization cohort safety study evaluating the effectiveness of the additional risk minimization measures for filgotinib (Jyseleca®) use in patients with moderate to severe active rheumatoid arthritis within European registries

CSP Version: 1.0 **Date:** 02-Feb-2022

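### Annex 4 gives baseline hyperlipidaemia and cardiovascular disease by rules built for follow-up outcomes, in conflict with Sections 6.1 and 8.3.1 and Table 3

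*Protocol*

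**What the plan says.** Protocol Section 8.3.1 states "Baseline variables are collected at index date" and adds that they include relevant medical history up to that date. For the risk of MACE, VTE and serious infection it refers the reader to Section 6.1 and Annex 4; Section 8.3.1.3 (BSRBR-RA) repeats the reference. Annex 4 carries the title "DEFINITION OF BASELINE DISEASES IN ARTIS, BIOBADASER, BSRBR-RA, DANBIO, AND RABBIT", then says that its code lists were created for the long-term safety PASS.

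The hyperlipidaemia row of Annex 4 reads "Patients who will initiate treatment with statins and other lipid-lowering drugs" for ARTIS and DANBIO. BSRBR-RA has the same rule in nearly the same words. For RABBIT the entry is "RABBIT: Hyperlipidemia reported as adverse event by the treating physician". BIOBADASER has lipid measures where clinical practice captures them. Table 3, by contrast, lists the ARTIS risk factor as "Use of treatment: Hyperlipidemia (Dx unavailable".

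On cardiovascular disease, Section 6.1 counts fatal and nonfatal events and states: "CVD comprises coronary heart disease (angina, myocardial infarction), congestive heart failure, cerebrovascular disease and peripheral artery disease". The Annex 4 MACE row for ARTIS and DANBIO begins "Combines MI, stroke, and fatal cardiovascular events: I00I99 as main cause of death" and adds I20.0, I21 and I60 to I64 from inpatient or outpatient care. The MedDRA column for the other three registries is split into a fatal-and-nonfatal list and a fatal-only list.

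**The concern.** The first objective is the proportion of filgotinib users at high risk of MACE, VTE or serious infection at baseline. Hyperlipidaemia and history of CVD are MACE risk factors in all five registry tables (Tables 3, 4, 6, 7 and 8). A factor defined by what happens after the index date is not a baseline factor, and a term that counts only when fatal cannot describe the history of a living patient who is starting treatment. If the annex is programmed as printed, both factors would be undercounted. Because the two columns and the single registries use different rules, part of any difference between registries would reflect coding, not prescribing.

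**Working it through.** No arithmetic decides this point. The one stated figure nearby, in Section 8.5, is the standard error for a 10% proportion at high risk of MACE with 300 users. It reproduces: sqrt(0.10 × 0.90 / 300) = 1.73%, with a 95% CI of 6.6% to 13.4%. The concern leaves it unchanged, since it is about what is counted and not about precision. The check is therefore a comparison of definitions.

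**Step 1: hyperlipidaemia against the baseline rule (on or before index).**

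| Registry | Risk-factor table | Annex 4 rule | Fits the baseline rule? |
|---|---|---|---|
| ARTIS | Table 3: treatment use | future start of a lipid-lowering drug | No; also contradicts Table 3 |
| DANBIO | Table 7: hyperlipidaemia | future start | No |
| BSRBR-RA | Table 6: hyperlipidaemia | future start | No |
| RABBIT | Table 8: hyperlipidaemia | adverse event report | Only if the report precedes index |
| BIOBADASER | Table 4: hyperlipidaemia | lipid measures, if captured | No conflict in timing |

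Take two patients under the drug-start rule, with the index date as its anchor. One has taken a statin for years and continues it: no start lies ahead, so the patient does not qualify. The other is untreated at index and starts a statin during follow-up: this patient does qualify. The rule excludes the prevalent case and admits the later one.

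**Step 2: nonfatal disease in Section 6.1 against the Annex 4 MACE row.**

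| Section 6.1 component | MedDRA column, nonfatal | ARTIS/DANBIO column, nonfatal |
|---|---|---|
| Myocardial infarction | counted | counted |
| Angina | no term in either list | only the unlabelled code I20.0 |
| Congestive heart failure | not counted (fatal only) | not counted (death only) |
| Cerebrovascular disease | stroke terms counted, but Cerebral infarction is fatal only | I60 to I64 counted |
| Peripheral artery disease | Peripheral arterial occlusive disease is fatal only | not counted (death only) |

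Both columns are narrower than Section 6.1, and they differ from each other. Within the MedDRA column, ischaemic, embolic and thrombotic cerebral infarction count when nonfatal, while the general term Cerebral infarction does not.

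**Step 3: is there another definition to fall back on?** Annex 4 ends with a table of other medical history. It covers malignancy, infection, renal impairment, joint prosthesis, diabetes and myocardial infarction. It has no row for hyperlipidaemia, and none for CVD beyond myocardial infarction.

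**Step 4: VTE.** The row label and Section 6.1 both say DVT and PE. The five MedDRA terms agree. The ARTIS/DANBIO column prints 14 codes without labels, including "I81.0, I82.0, I82.1, I82.2, I82.3, I82.8, I82.9". The protocol does not say what these codes mean, so the comparison cannot be completed from the document.

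**The case against.** The strongest reply is that the cross-reference in Section 8.3.1 follows the words for the three outcomes, so Annex 4 defines outcomes, while the risk factors stand in Tables 3, 4, 6, 7 and 8. A fatal-only split is ordinary in an outcome list, and no sentence says that history of CVD is coded with the MACE row. This has force: the second part of the point must stay conditional. It does not remove the ambiguity, because the annex title says baseline diseases and Section 6.4 promises to report whether patients had already experienced these outcomes at baseline.

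Other replies also carry weight:

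- The MedDRA column is marked as provisional, with the final list to follow. That caveat does not head the ARTIS/DANBIO column.
- A RABBIT adverse event can precede the filgotinib index date if the patient entered the registry on an earlier drug. It remains a follow-up style of record, not a baseline history item.
- Heart failure, and acute infarction or ischaemic stroke, appear separately in most registry tables. They are assigned there to the VTE column, not to MACE.
- Differences in data availability between registries, and endpoint misclassification, are acknowledged in Sections 8.3.1 and 8.9. That does not excuse a rule that contradicts the protocol's own time window.

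A reader might infer that the VTE lists contradict Section 6.1 outright. The documents do not support this: the MedDRA terms agree with it, the ICD codes are unlabelled, and Section 6.1 introduces DVT and PE with a non-exclusive verb.

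**Conclusion.** The point holds in two parts. First, the hyperlipidaemia row conflicts with Section 8.3.1 for ARTIS, DANBIO and BSRBR-RA, and for ARTIS with Table 3 as well. RABBIT's rule is ill suited to baseline, and BIOBADASER is not affected by the timing conflict. Read literally, the drug-start rule leaves out patients already treated at index. Second, the MACE lists are narrower than Section 6.1 for nonfatal heart failure, peripheral artery disease, angina and one general stroke term. If they are used for history of CVD, that factor is undercounted, and unequally so across registries.

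Only the direction is established. It rests on two assumptions: that the annex wording is applied as printed, with the index date as anchor, and, for the second part, that the MACE row is used for history. It is tempting to attach a number. Assuming 15% to 35% of patients treated at index and 2% to 5% new starts a year over one to two years, the literal rule would record 2% × 1 = 2% to 5% × 2 = 10%. None of these inputs, nor the window, is in the protocol, so this is no estimate of the error. Nor does it show the effect on the overall proportion at high risk, to which age, sex, smoking, diabetes and hypertension also contribute. A claim that every prevalent statin user will be misclassified would likewise go too far, since a registry may follow Section 8.3.1 or Table 3 instead.

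**What to change.** Add baseline-specific rows to Annex 4:

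- **Hyperlipidaemia:** a recorded diagnosis, or any lipid-lowering use or dispensing, on or before the index date, as available in each registry.
- **History of CVD:** the Section 6.1 components recorded on or before the index date, with the same components in both columns and no fatal-only split.

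Label the present lists as follow-up outcome definitions for the safety PASS, and state in Section 8.3.1 which rows serve as baseline history. For VTE, ask the sponsor only to confirm that the ARTIS/DANBIO codes match the row's own label and the MedDRA column.

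The cost is an annex edit and re-coding of two variables from data already held. The drawback is that the baseline lists would no longer be identical to those of the linked safety PASS.
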